An intervention to Promote Positive Peer Relationships and Reduce Prejudice and Bias in Childhood

Analysis Plan

16 July 2025

1. Hypotheses

- 1.1. We expected that compared to the control condition, participants in the treatment condition would:
 - 1.1.1. report higher **school belonging, peer support, and teacher support** at posttest.
 - 1.1.2. report lower levels of **personal experiences with exclusion** at posttest.
 - 1.1.3. report higher **contact with diverse peers** at posttest.
 - 1.1.4. report higher **desire to play with diverse peers** at posttest.
 - 1.1.5. more negatively **evaluate exclusion** at posttest.
 - 1.1.6. have higher **high-status occupation expectations** about marginalized groups (girls, Black peers, Latine peers) at posttest.
 - 1.1.7. make more positive **trait attributions** of diverse peers at posttest.
 - 1.1.8. have higher **expectations of inclusivity** of different peer groups at posttest.
 - 1.1.9. have more positive **math and science competency beliefs** about marginalized groups (girls, Black peers, Latine peers) at posttest.
- 1.2. We expected treatment effects to vary by participant race/ethnicity for school belonging, peer support, teacher support, personal experiences with exclusion, contact with peers of different race/ethnic groups, desire to play with peers of different race/ethnic groups, evaluations of exclusion of different race/ethnic groups, high status occupation expectations about marginalized racial groups, beliefs about the inclusivity of different race/ethnic groups, math and science competency beliefs about different race/ethnic groups, and trait attributions of different race/ethnic groups.
- 1.3. We expected treatment effects on the above listed outcome measures to vary by grade. Older children may exhibit greater change on these measures due to more awareness of group dynamics. However, a previous iteration of this program (conducted with a more racially homogeneous sample) found that compared to 5th graders, 3rd graders showed more change from pre to posttest.
- 1.4. Exploratory hypotheses: We tested for school effects due to differences in their racial composition. We also examined 2-way treatment interactions with school, race, and gender to determine whether the program was more effective for certain child demographic groups.

2. Measured variables

1. School belonging*
2. Peer support*
3. Teacher support*
4. Personal experiences with exclusion*
5. Reported contact
6. Desire to play

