7. Evaluations of exclusion
8. High status occupation expectations
9. Positive trait attributions*
10. Expectations of inclusivity
11. Math and science competency beliefs

**Indicates mean composite variable*

Measures also included in analyses, depending on model selection:

- Participant race/ethnicity (parent report)
- Gender (parent report)
- Grade level (3, 4, 5)
- Pretest measure for the respective outcome model was included as a control in each model
- School

Analysis Procedure

We first examined ICCs for classroom level and school level to determine if multilevel modeling was needed and conducted model comparisons to determine if classroom, school, and sex should be included as fixed effects. We selected models for each outcome variable based on lowest AIC and BIC.

We also conducted exploratory factor analyses on reported contact measures, desire to play measures, and evaluations of exclusion to determine if creating composite measures was most appropriate for analysis.

For all models, we included school, classroom, and gender if model comparisons indicate, using the model with lowest AIC and BIC for a given outcome variable.

We conducted multiple regression linear regression for all **composite variables**, using the base model:

```
lm(posttest DV ~ pretest DV + treatment*grade + race-ethnicity)
```

For all individual items for **reported contact, desire to play, evaluations of exclusion, expectations of inclusivity, and math/science competency beliefs**, we conducted ordinal logistic regression using the base model:

```
polr(posttest DV ~ pretest DV + treatment*grade + race-ethnicity)
```

For **high status occupation expectations**, we examined outcome distributions to determine if it is appropriate to collapse response options by stimuli gender and/or race. We conducted multinomial logistic regression using the base model:

```
multinom(posttest DV ~ pretest DV + treatment*grade + race-ethnicity)
```

Exploratory Analyses

For the above models, we tested the model removing the grade*treatment interaction, if it is not significant, to isolate the treatment effect. We also tested interactions of treatment*grade and treatment*gender to determine if the treatment was more effective for certain demographic groups.

Inference criteria

We considered predictors significant at a *p*-value of .05. We used Bonferroni adjustment for multiple groups pairwise comparisons.

Data exclusion

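### Hypothesis 1.1 is tested on 11 outcomes at .05 each with no adjustment across them, and its overall treatment contrast is stated only when the treatment-by-grade interaction is not significant

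*SAP*

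**What the plan says.** SAP section 1.1 opens with "We expected that compared to the control condition, participants in the treatment condition would" and lists nine directional statements. Together they cover all 11 outcomes numbered in section 2. No outcome is called primary there or in the protocol's Aims 2 and 3.

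Inference criteria has two sentences. The first is "We considered predictors significant at a" p-value of .05. The second is "We used Bonferroni adjustment for multiple groups pairwise comparisons".

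Under Analysis Procedure, composites use "lm(posttest DV ~ pretest DV + treatment*grade + race-ethnicity". For the individual items of five outcomes, "we conducted ordinal logistic regression using the base model", with the same right-hand side. The occupation outcome uses a multinomial model, again with treatment crossed with grade. School, classroom and gender may be added according to AIC and BIC.

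Under Exploratory Analyses, the interaction is removed "if it is not significant, to isolate the treatment effect". Section 1.3 states: "We expected treatment effects on the above listed outcome measures to vary by grade". Table 1 of the protocol has two posttests, at weeks 10 and 18; the SAP does not say which one section 1.1 refers to.

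**The concern.** There are two gaps, and both bear on what may be concluded from the section 1.1 tests.

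**Error across outcomes.** Aims 2 and 3 each ask whether the program worked on a broad construct that is measured in several ways. No rule says how mixed results across those measures answer the question. The Bonferroni sentence concerns comparisons among groups, perhaps including within-grade follow-ups, but not the set of outcomes. Eleven may also undercount the tests, because five outcomes can be modelled item by item and the number of items is not given.

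**Which term is the test.** With treatment crossed with grade as a factor under R's default coding, the treatment coefficient is the effect in the reference grade. A single overall effect appears only after the interaction has been found non-significant and dropped. The SAP therefore states no contrast for section 1.1 in just the situation that section 1.3 predicts.

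**Working it through.** The documents give no power, familywise error rate or sample-size calculation, so there is no planned figure to reproduce.

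**Inputs from the documents:** 11 outcomes (SAP section 2); .05 per predictor (Inference criteria); three grades (SAP section 2).

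**Assumptions:** two-sided tests; correlations among test statistics of 0, 0.3, 0.5 and 0.7; balanced arms; equal grade sizes; 80% power for the grade-averaged effect at .05.

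**1. Chance of at least one significant result if the program has no effect**

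If independent, this is 1 − 0.95^k. For k = 11 it is 1 − 0.95^11 = 0.431. For correlated outcomes the figures come from simulating equicorrelated normal statistics (400,000 draws).

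| Tests counted | Independent | 0.3 | 0.5 | 0.7 |
|---|---|---|---|---|
| 11, either direction | 43% | 37–38% | 30% | 22% |
| 11, favourable direction only | 24% | 19% | 15% | 11% |

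The second row uses 1 − 0.975^11 = 0.243 for independence and treats all 11 as signed tests. Item-level models would raise both rows.

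**2. What the two-step rule does to the section 1.1 test (linear models)**

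Suppose the interaction is tested jointly on 2 df. If it is not significant, the overall effect from the reduced model is used. If it is significant, the reference-grade coefficient is used. The second branch is a supposition, since the SAP states nothing for it.

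The averaged effect has noncentrality 1.96 + 0.84 = 2.80. Each grade-specific effect has a standard error √3 times as large. The averaged estimate is independent of the interaction statistic, so the first branch contributes P(interaction not significant) × 0.80.

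- *Equal effects in all grades.* The first branch gives 0.95 × 0.80 = 0.76. Adding the second branch, the simulated total is about 78%.
- *Effects of 0, 1 and 2 times the average.* The interaction noncentrality is (1² + 0² + 1²) × 2.80² / 3 = 5.23, so the interaction is significant about 52% of the time. The first branch gives 0.48 × 0.80 = 0.38.
  - Zero effect in the reference grade: the second branch adds about 0.03, for a total of about 41%.
  - Largest effect in the reference grade: the second branch adds about 0.51, for a total of about 89%.

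The grade-averaged contrast has 80% power in all three cases. The rule's behaviour therefore depends on which grade is the reference, and the SAP does not say.

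**3. Holm in two families**

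For illustration, take 4 tests (school belonging, peer support, teacher support, personal experiences with exclusion) and 7 tests (the remaining outcomes). Under no effect and independence, the chance of any false positive is 1 − (1 − .05/4)^4 × (1 − .05/7)^7 = 0.096. The upper bound is .05 + .05 = .10.

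Power at the strictest step is Φ(2.80 − z), with z the two-sided critical value:

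- 4 tests, .0125: Φ(2.80 − 2.50) = 0.62
- 7 tests, .0071: Φ(2.80 − 2.69) = 0.54
- 22 tests, .0023: Φ(2.80 − 3.05) = 0.40

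The last line assumes four items for each of the five item-level outcomes and no composites, so 2 + 5 × 4 = 22 tests.

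**The case against.** **On multiplicity.** The nine statements are separate, named hypotheses. Each keeps its own 5% error, and whether separate hypotheses need joint control is debated. This stands for outcome-specific claims. A reader might infer that the trial carries a 43% false-positive rate. The documents do not support that. The SAP has no rule that one significant outcome is enough, and 43% needs independence, which is implausible for measures such as belonging, peer support and teacher support reported by the same children. The inflation applies to a summary claim about an aim, and the correlated range is the relevant one.

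**On the contrast.** The SAP is not silent: when the interaction is not significant, the reduced model gives one treatment coefficient. A reader might infer that section 1.1 has no defined test at all, or that it always rests on a single grade and so loses most of its power. The drop step rules that out, since with equal grade effects power is about 78% against 80%. Nor does anything show that the analysts read the default coefficient as the section 1.1 result, or that grade was entered as an uncentred number. What remains is that the step is labelled exploratory, depends on the data, and leaves section 1.1 without a contrast when the interaction is significant.

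**On timing.** The SAP is dated July 2025 and written in the past tense, so a new family or contrast may be post hoc. That affects how the change is labelled, not whether it is useful.

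**Conclusion.** The point holds, as an inexpensive improvement rather than a flaw that invalidates the trial. The textual gaps are certain: 11 outcomes, none primary, no adjustment across them, and no section 1.1 contrast when the interaction is significant.

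The size is conditional. The 22% to 38% for a false claim applies only if any significant outcome is read as support for effectiveness, and it rests on assumed correlations of 0.7 to 0.3. If only favourable results count, the corresponding range is 11% to 19%. The 78%, 41% and 89% powers rest on equal grades, an assumed 80% for the averaged effect, and the supposition that the reference-grade coefficient would be used after a significant interaction. They show a test whose meaning and power depend on the data and on an unstated reference grade, not a uniform loss of power.

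**What to change.** In Inference criteria, with a cross-reference from Analysis Procedure:

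1. Define the section 1.1 test for each outcome or item as the treatment effect averaged over grades with stated weights, for example equal weights. Take it from the selected model, including any school, classroom or gender terms, with treatment-by-grade kept whatever the interaction test shows. Use the log-odds scale for ordinal models and one stated directional contrast for the multinomial outcome. State whether Posttest I or Posttest II is meant.
2. Apply Holm to these tests within stated families, for example Aim 2 and Aim 3, counting every item-level test run. Say that the allocation of outcomes to aims is the SAP's own choice, because the protocol does not give one.
3. Report adjusted and unadjusted p-values, and base aim-level claims of effectiveness on the adjusted ones. State that two families allow up to about 10% familywise error, and that this covers the section 1.1 tests only, not the interaction tests of sections 1.2 and 1.3.
4. Label these choices post hoc if data had been seen when they were made.

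The cost is a few sentences, one averaged contrast per model pooled over the 30 imputed datasets, and a p-value adjustment; no new data are needed. The downside is the power loss at the strictest Holm step shown above, which grows if items are tested singly. Later steps are less strict, and the unadjusted results stay on view.

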Aim #3: The third aim of the proposed project was to test whether a class-based intervention (class-based curriculum tool with classroom discussion, *Developing Inclusive Youth (DIY)*) was effective in *reducing prejudicial attitudes and behaviors*, relative to children in the business as usual (control) condition.

Method

Settings and Participants. Participants were 3rd, 4th, and 5th grade students (8 – 11 years of age), representing a range of racial and ethnic groups (European-American, African-American, Latino/a, Asian-American, and Multiracial), $N = 885$. The study was implemented in a large public school district in the Mid-Atlantic region of the U.S.

Procedure and Scenarios. The animated and narrated computer based tool was accessed through a password-protected internet link housed at the University of Maryland under the supervision of the P.I. Unique login IDs are distributed to children whose parents have given consent for participation. Participating students had a laminated card with the name and login ID

on it which was distributed to them at the beginning of each session (and retrieved at the end of each session). And these login IDs allowed for the tracking of responses over the course of the 10-week program.

Table 1. Design of the Pre-test, Intervention Program, BAU Group, and Post-test

Design	Screening 1	Block A	Screening 2	Block B	Screening 3
	Week 1	Weeks 2- 9	Week 10	Weeks 11-17	Week 18
Intervention Program	Pretest Administered	Program	Posttest I Administered	BAU	Posttest II Administered (follow-up)
Control Group (Business as Usual)	Pretest Administered	BAU	Posttest I Administered	BAU	Posttest II Administered (follow-up)

The **control group** was Business-As-Usual. The **intervention program** included children using the web-based curriculum tool for 15 minutes in the classroom followed by a 30-minute discussion period once a week for eight weeks. During each intervention session children would respond to one of the eight scenarios (with a new target group each week). This was a 10-week program.

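### Plain Bonferroni for the pairwise group comparisons is valid, but Holm's procedure gives the same 5% guarantee with slightly more power

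*SAP*

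**What the plan says.** The SAP's Inference criteria hold two rules. The first covers model terms: "We considered predictors significant at a *p*-value of .05". The second covers comparisons among groups: "We used Bonferroni adjustment for multiple groups pairwise comparisons". The second rule names no factor and does not say which comparisons form one family.

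The factors that could have more than two levels are:

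- **Grade.** Three levels (SAP, Measured variables).
- **Race/ethnicity.** Five groups are listed in the Protocol (Method, Settings and Participants), for a total of 885 children.
- **School.** The number of schools is not stated.

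Two hypotheses lead to such comparisons. On race/ethnicity (1.2) the SAP says "We expected treatment effects to vary by participant race/ethnicity", and on grade (1.3) "We expected treatment effects on the above listed outcome measures to vary by grade". The base model for composite outcomes is "lm(posttest DV ~ pretest DV + treatment*grade + race-ethnicity"), and the ordinal and multinomial models have the same right-hand side. Grade therefore interacts with treatment in the base models, while race/ethnicity enters only as a main effect.

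**The concern.** Bonferroni holds every pair to the same strict threshold, even after some pairs have clearly been separated. Holm relaxes the threshold after each rejection and keeps the same family-wise guarantee, so the plan gives up some power without a stronger guarantee in return.

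The comparisons affected bear on named hypotheses. Hypothesis 1.3 sets out rival expectations: older children may change more, yet a previous iteration saw more change in 3rd than in 5th graders. A significant interaction alone does not settle the direction; the between-grade contrasts do. These contrasts also rest on less data than the overall treatment comparison.

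**Working it through.** The documents give no power figure or adjusted alpha for these comparisons, so there is no plan figure to reproduce.

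**Inputs from the documents.** Alpha .05; 3 grades; 5 race/ethnic groups; N = 885.

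**Assumed inputs.** Two-sided tests, SD 1, equal groups, 1:1 allocation within grade, design effect 1 or 2 for treatment-effect contrasts, and group differences of 0.1 to 0.5 SD.

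**Step 1: thresholds.** The number of pairs is k(k−1)/2.
- Three grades: 3 pairs. Bonferroni uses .05/3 = .0167 for each. Holm uses .0167, then .05/2 = .025, then .05.
- Five race/ethnic groups: 10 pairs. Bonferroni uses .05/10 = .005 for each. Holm starts at .005 and rises to .05.

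The first Holm threshold equals Bonferroni's and the later ones are larger. Holm therefore rejects everything Bonferroni rejects, and the two agree exactly on whether any pair is rejected.

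**Step 2: one case by hand.** Each grade has 885/3 = 295 children, or 147.5 per arm. The SE of a treatment effect within one grade is √(2/147.5) = 0.116. The SE of a difference in treatment effect between two grades is 0.116 × √2 = 0.165. For a 0.4 SD difference, z = 0.4/0.165 = 2.43. The Bonferroni critical value at .0167 two-sided is 2.394. Power per true pair is Φ(2.43 − 2.394), about 51%.

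**Step 3: simulation.** All-pairs z tests were simulated, with 400,000 runs for three groups and 100,000 for five. Entries are average power per truly different pair.

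| Case (true values in SD) | Bonferroni | Holm | Gain, points |
|---|---|---|---|
| Treatment effect by grade 0/0/0.4, design effect 1 | 51.4% | 54.5% | 3.1 |
| Same, design effect 2 | 24.9% | 26.6% | 1.8 |
| Treatment effect by grade 0/0.2/0.4, design effect 1 | 25.0% | 27.3% | 2.2 |
| Same, design effect 2 | 12.5% | 13.6% | 1.0 |
| Grade means 0/0.2/0.4 | 67.4% | 76.0% | 8.7 |
| Five groups 0/0/0/0/0.3 | 50.4% | 52.7% | 2.3 |
| Five groups 0/0/0.3/0.3/0.3 | 50.6% | 54.9% | 4.3 |
| Five groups 0/0.1/0.2/0.3/0.4 | 25.0% | 27.1% | 2.0 |

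The simulated 51.4% agrees with Step 2. In that first case:
- The chance of finding at least one true pair is 68.1% under both methods.
- The chance of finding both true pairs rises from 34.8% to 41.0%.
- The error on the one null pair rises from 1.7% to 2.8%, still below 5%.

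**Step 4: error control.** With no true differences, family-wise error is 4.4% for three groups and 4.0% for five, the same for both methods. In no run did Holm fail to reject a pair that Bonferroni rejected.

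**The case against.** The strongest objection is that nothing here is wrong. Bonferroni is valid and widely used, it is simple to report, and preferring Holm is a choice about efficiency. That stands, and it is why the point is only an improvement.

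A reader might go further in three ways that the documents do not support.

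- **That real group differences are being missed.** No effect size, SD, group size or power is given, so this cannot be asserted. Under assumed inputs the loss is usually a few points per pair. The treatment coefficient and the treatment-by-grade terms are judged at .05 as model predictors, so the Bonferroni sentence cannot hide the main treatment effects.
- **That these pairs show in which grade or group the program worked.** Between-grade contrasts show whether effects differ. Where the program worked is answered by treatment versus control within each grade. For race/ethnicity, the base models carry only a main effect, so pairwise comparisons from them concern outcome levels.
- **That three grades need no adjustment once an overall grade test is significant.** This holds only if the gate is the treatment-by-grade interaction and the comparisons are the three between-grade contrasts of treatment effect. If the gate is the grade main effect and outcomes differ by grade, the gate nearly always opens. The three contrasts are then tested unadjusted, and simulated family-wise error is about 12% when all are null. Applied to within-grade treatment effects, an interaction gate gives about 8% when one grade has a 4-SE effect and the other two have none.

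Two further points stand. Bonferroni's realised error is lower than Holm's when only some pairs differ, although both keep to 5%. And no adjustment is stated across the 11 listed outcomes; if these were independent and each tested at .05, the family-wise error would be 1 − 0.95^11 = 43%. That is a separate and larger gap, and Holm within each outcome does not close it.

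**Conclusion.** The point holds as an optional improvement. Holm is never less powerful than Bonferroni under the same 5% guarantee; that is a general property and needs no assumption about this trial.

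The size does rest on assumptions. With SD 1, equal groups, and the effects and design effects listed, the gain is roughly 1 to 4 points of average power per truly different pair. The exception is about 9 points, when all three grade means are well separated. The benefit lies in finding second and later differences, not the first. Unequal group sizes or other effects would move these figures.

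**What to change.** Replace the Bonferroni sentence under Inference criteria with:

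*Pairwise comparisons among grades, race/ethnic groups and schools use Holm-adjusted p-values within each factor and outcome.*

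Holm needs only p-values, so it applies directly to the pooled results of the linear, ordinal and multinomial models. The wording also fixes the family of comparisons.

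Do not add a rule that tests grade pairs at .05 after an overall test. If such a rule is used at all, the SAP must name the treatment-by-grade interaction as the gate and limit the rule to the three between-grade contrasts of treatment effect.

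**Cost.** One sentence and one software option, with two caveats. Simple simultaneous intervals will not match the Holm decisions exactly; Bonferroni intervals can still be shown. And the SAP is written in the past tense, so results may already be known. Moving to a less strict rule should then be disclosed as such, with the Bonferroni results beside the Holm results. No pair significant under Bonferroni would be lost.

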Children who could not independently complete the survey and had no trained adult available to assist them complete the pre-test and/or post-test were excluded from the sample and the subsequent analyses.

Missing data (optional)

We conducted imputations using predictive mean matching to address missing values. We imputed 30 datasets using the “mice” package in R. Demographic variables (grade, classroom, condition, gender, and school) were included as predictors, while pretest scores, posttest scores, and race were included as both predictors and imputed values. All analyses were conducted on the 30 imputed datasets individually and the pooled results were reported.

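### The imputation model lists no treatment interaction; run as listed, it dilutes the treatment-by-race and treatment-by-gender estimates that the SAP goes on to test

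*SAP*

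**What the plan says.** The Missing data section of the SAP describes predictive mean matching with 30 imputed datasets. The fully observed predictors are given as "Demographic variables (grade, classroom, condition, gender, and school) were included as predictors". For the rest, "pretest scores, posttest scores, and race were included as both predictors and imputed values". No product term and no split by arm is mentioned. The section closes with "All analyses were conducted on the 30 imputed datasets individually and the pooled results were reported"; no complete-case analysis is described.

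The interactions at issue are stated elsewhere in the SAP. Hypothesis 1.2 opens with "We expected treatment effects to vary by participant race/ethnicity for school belonging" and continues through a long list of outcomes. Hypothesis 1.4, labelled exploratory, says "We also examined 2-way treatment interactions with school, race, and gender". The Exploratory Analyses section says "We also tested interactions of treatment*grade and treatment*gender". The base models in the Analysis Procedure contain one interaction, treatment-by-grade, with race as a main effect. Besides the linear models for composites, single items were handled thus: "we conducted ordinal logistic regression using the base model"; and for occupation expectations, "We conducted multinomial logistic regression using the base model".

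The Protocol gives N = 885 (Settings and Participants) and describes randomisation within schools, without saying whether classrooms or children were assigned. Neither document gives the share of missing post-tests or race, or the imputation formula.

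**The concern.** An imputation model should contain at least the structure that the analysis model tests. If condition, race and gender enter only as main terms, an imputed post-test reflects one common treatment effect whatever the child's race or gender. The pooled interaction is then a mixture of observed children, who carry the true interaction, and imputed children, who carry about none. Classroom terms cannot repair this, because race and gender vary within classrooms. Imputing race without condition-by-score terms adds a second dilution to treatment-by-race.

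At stake is how a null subgroup result is read. If Hypothesis 1.2 or treatment-by-gender came out non-significant, a reader could not tell how much of that came from the imputation.

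**Working it through.** **Inputs.** From the documents: N = 885; predictive mean matching; 30 imputations; significance at .05. The plan states no missing share, effect size or power, so there is no figure to reproduce. Everything else is assumed. The main simulation used 48 classrooms in 6 schools, five race groups (35/20/20/15/10%, interaction in a 20% group), classroom ICC 0.05, pretest slope 0.5 and 5 donors. The interaction was 0.30 SD for linear outcomes and 0.55 on the log-odds scale for a five-category ordinal item and a three-category outcome. The analysis model held treatment-by-grade, -race and -gender jointly. A second simulation used 42 classrooms, two race groups (40% in one), interaction 0.4 and 10 imputations.

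**Step 1: approximation.** Let group g have true effect τ_g and post-test missing share m_g (the same in both arms), and let τ̄ be the common effect that a main-terms imputation assigns. The pooled effect in g is about (1 − m_g)τ_g + m_g τ̄. With equal shares m, the contrast between two groups is (1 − m)(τ_g − τ_h), so the share kept is 1 − m: 90, 80 and 70% at m = 0.10, 0.20 and 0.30.

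**Step 2: simulated share kept, race complete, post-test wholly missing.**

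| Outcome model | Race, 10/20/30% missing | Gender, 10/20/30% missing |
|---|---|---|
| Linear | 90/80/69% | 90/80/70% |
| Ordinal | 89/78/66% | 91/80/70% |
| Multinomial | 91/81/71% | 90/81/71% |

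Monte Carlo error is at most 1.2, 2.5 and 2.0 points respectively. The second simulation (linear) lost 10.1/19.7/28.9% for race and 9.0/19.7/30.9% for gender. With the product terms added, its loss at 20% was 0.1% and −0.4%.

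**Step 3: race imputed as well.** If a share r of race is also missing, independently, the expected loss for race is 1 − (1 − m)(1 − r).

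| m, r | Formula | Simulated loss, race | Simulated loss, gender |
|---|---|---|---|
| 0, 10% | 1 − 0.90 = 10% | 9.3% | 0.3% |
| 10%, 10% | 1 − 0.90 × 0.90 = 19% | 18.0% | 9.5% |
| 20%, 10% | 1 − 0.80 × 0.90 = 28% | 30.1% | 19.7% |
| 20%, 20% | 1 − 0.80 × 0.80 = 36% | 35.5% | 20.3% |

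A further check of the 20%/10% case lost about 27% for race.

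**Step 4: what moves the size.** If the affected race group has 1.5 times the average missing rate and low pretests are missing more often, race keeps 86.5/73/59%, a loss of 13.5/27/41%. If 20% missingness is concentrated in treated children of one race group, the race loss is 27.7%. In the other direction, one observed post-test with residual correlation 0.5 and the same interaction raises race to 94/90/85% kept. Three such post-tests cut the loss at 20% to 5.3% (race) and 4.2% (gender). If those are missing too, it returns to 19.1% and 16.5%.

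**Step 5: distortion.** By step 1, two groups with the same true effect τ but unequal missing shares differ by (m_h − m_g)(τ − τ̄). In a simulation with five race groups, 40% missing in one and 10% elsewhere, and an effect of 0.6 SD in two groups (one of them the 40% group) and 0 in the rest, the contrast between those two was −0.114 (Monte Carlo SE 0.007). Complete-case gave 0.000. The formula agrees if τ̄ = 0.6 − 0.114/0.30 = 0.22. The rejection rate for this contrast was 3.4%.

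**Step 6: inference, linear outcome, true interaction 0.30 SD.**

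| Power at 10/20/30% missing | As listed | Product terms | Complete-case |
|---|---|---|---|
| Race | 31.9/21.4/12.0% | 40.9/36.7/32.4% | 40.7/37.1/31.7% |
| Gender | 60.6/46.8/30.6% | 69.5/62.2/55.9% | 67.8/62.1/57.0% |

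With no true interaction and 20% missing, false positives were 1.8% (race) and 2.0% (gender) as listed, against 5.6% and 5.4% with product terms.

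**Step 7: treatment-by-grade.** If each classroom has one grade and one arm and classroom enters as a factor, its indicators already span this interaction: 100–101% is kept. With classroom as a numeric code it is 90/81/71%; with children assigned individually, 90/80/69%.

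**The case against.** The case against has real weight. The Missing data section names variables, not a formula, so product terms may have been used and not reported. That stands, and it makes the point conditional. The missing share is unknown, and with 11 outcomes entering as predictors the loss could be small where only some of a child's scores are missing. That also stands; it does not help a child with no post-test at all.

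The error is conservative and sometimes harmless. At 0.30 SD and 20% missing, the race bias is 0.30 × 0.20 = 0.06, a third of the pooled SE (0.06/0.181 = 0.33); coverage is 97.4% and RMSE is lower as listed (0.160 against 0.180). At 0.50 SD and 20% the balance turns for gender: RMSE 0.146 against 0.131, coverage 92.5% against 95.3%. Power for race is also low after the fix, so much of the difficulty in reading a null is sample size.

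Finally, no treatment-by-race model is written out in the Analysis Procedure. But Hypotheses 1.2 and 1.4 state that interaction, and treatment-by-gender appears in two places.

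A reader might infer that the overall share of imputed post-tests caps the loss for race. It does not: race is itself imputed, and missingness may be uneven. A reader might also infer that every race contrast simply shrinks; step 5 shows otherwise.

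**Conclusion.** The point holds, with medium confidence, and is worth correcting. As described, the imputation is less rich than the analyses run on it. If it was run that way, treatment-by-gender loses about the share of post-tests imputed, and treatment-by-race up to about the share of children with post-test or race imputed. Concentrated missingness raises the loss and correlated observed post-tests lower it. The true size cannot be found from the documents. The 90/80/70% figures rest on assumed missing shares and complete race, and the power levels rest on assumed group sizes and effects.

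Three stronger readings are not supported. The documents do not show that interactions were left out; they show only that none is listed. Nothing here suggests false-positive subgroup claims: no inflation was seen, although the no-interaction case was run only at 20% missing. The main treatment effect is not at issue, and treatment-by-grade is largely protected if whole classrooms were assigned and classroom was a factor. Treatment-by-school was not examined.

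**What to change.** First, state the imputation model in full. If interaction terms or imputation by arm were used, saying so settles the matter. If not, run mice separately by condition. Alternatively, add condition-by-race, condition-by-gender and condition-by-grade terms when imputing post-tests, and condition-by-score terms when imputing race. Then re-run the interaction models.

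Report the shares of post-test and race imputed, by arm. Give a complete-case analysis of the interactions as a sensitivity check. State the unit of assignment and whether classroom was a factor or a numeric code in the imputation.

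The cost is a re-run, with no new data, and more variable interaction estimates. For treatment-by-race at 10/20/30% missing, the pooled SE goes from 0.173/0.181/0.189 to 0.173/0.184/0.197, and the between-sample SD from 0.154/0.148/0.140 to 0.169/0.180/0.194. RMSE therefore rises when the true interaction is small. The repair is near complete for linear outcomes (98–100% kept) but less so for race on ordinal items: 97/94/90% with product terms, 97/96/91% by arm.
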